2.2.2 Repeat Dosing

In order to ensure the safety of repeat dosing, specifically in regards to AEs and electrolyte changes (such as sodium and potassium levels), and to ensure subjects with a demonstrated need receive treatment, 1 repeat dose will be allowed for all dosing groups. The repeat dose will

consist of repeating the same dose, and will occur between 2 and 24 hours after the initial dose, if the repeat dosing criterion is met. The repeat dosing criterion is defined as: at least 2 hours, but no more than 24 hours, post dosing and a FiO_2 level of at least 0.35.

If, in the opinion of the PI, repeat dosing would compromise the safety of the subject, repeat dosing will not occur.

2.2.3 Sample Size Justification

The number of subjects randomized (8 in each active group and 8 in each control group) is considered sufficient to establish safety and tolerability before proceeding to the next higher dose. A total of approximately 32 subjects assigned to the active arm and approximately 32 subjects for the control arm for the entire study is considered sufficient to assess the overall safety and tolerability and to select safe and well-tolerated doses. Statistical sample size calculations were not performed.

2.2.4 Study Schedule

Protocol Event Schedule Summarization

Measurement/Procedure	Study Period			
	Screening	Primary Observation	Extended Observation	Final Observation
		Days 1-2	Days 3-7	Day 8 to 36 Weeks PMA Final Visit (36w PMA)
Informed Consent/HIPAA	X			
Inclusion/Exclusion Criteria	X			
Demographics	X			
Maternal/Birth History ¹	X			
Physical Exam	X			X
Chest Radiograph ²	X			
Randomization		X		
Study Treatment		X		
Body Weight		X ¹		
Defecation		X		
Vital Signs		X ³	X ³	
Monitoring of SpO ₂ ⁴		X	X	
Monitoring of PCO ₂ ⁵		X		
Resp. Support and O ₂ Delivery	X	X	X	X ⁶
Serum Electrolytes		X ⁷		
Gastric Liquid Volume ⁸		X		
Peri-Dosing Events ⁹		X		
Adverse Events		X	X	X
Adverse Device Effects		X		
Concomitant Medication		X	X	X

Note: Day 1 for all subjects is the day of study randomization.

¹ Birth weight is captured in birth history. The first body weight obtained after randomization is recorded in the eCRF.

² A chest radiograph prior to intubation is required if such a procedure does not delay or compromise the care of the subject.

⁴ Vital signs will be documented ≤ 15 minutes (± 5 minutes) prior to randomization. For the active arms, vital signs will be documented every 5 minutes (± 2 minutes) during dosing for Dosing Group I and II; every 15 minutes (± 5 minutes) during dosing for Dosing Group III and IV. For the control arms, vital signs will be documented at 15 minutes (± 5 minutes) post randomization. In addition, for all subjects, record at 1, 3 (± 15 minutes), 6, 12 (± 1 hour), 18, 24, 36 and 48 hours (± 2 hours) post randomization and daily at 0800 (± 2 hours) on days 3 to 7.

⁵ Continuous monitoring of SpO₂ is initiated at the time of randomization and continued until completion of Study Day 7.

⁶ Continuous trancutaneous PCO₂ monitoring for all subjects is to be initiated following randomization and at least 30 minutes prior to the start of ADS delivery, and continued for 72 hours post randomization.

⁷ Only the date and time of the initiation and discontinuation of ventilator and pressure support is to be documented in the study eCRF beyond Study Day 7.

⁸ Serum electrolytes are to be evaluated 24 hours from randomization (± 6 hours)

⁹ Gastric liquid volume will be assessed 30 minutes (± 15 minutes) following completion of study treatment administration. Enteral feedings are to be held during administration and ≥ 1 hour following completion of study treatment.

¹⁰ Peri-dosing events are defined as any AE with an onset time ≤ 2 hours from the time of initiating study treatment.

3 STUDY SUBJECT CHARACTERISTICS

3.1 DEMOGRAPHICS AND BASELINE CHARACTERISTICS

3.1.1 Demographics

Continuous variables (eg, gestational age, birth weight) will be summarized using mean, standard deviation (SD), median, minimum, and maximum. Categorical variables (eg, sex, race, ethnicity) will be summarized using frequency and percent.

Race categories with small numbers (frequencies of 0 or 1 or percentages of < 10%) will be combined as 'Other' for summary displays.

3.1.2 Birth and Maternal History

Mode of delivery (vaginal, c-section), type of birth (single, multiple), Apgar score at 1 and 5 minutes, and incidence of congenital anomalies will be summarized using frequency and percent.

The incidence and type of ruptured membranes, incidence of clinical chorioamnionitis, and the incidence and number of doses of antenatal steroids will be summarized using frequency and percent.

3.3 STUDY AND CONCOMITANT MEDICATION

3.3.1 Compliance

Compliance summary for this study is not applicable as all subjects will be administered at least one dose by study staff in the NICU.

3.3.2 Number of Doses

The number of doses (treatments) received by subjects in the active arms will be summarized.

3.3.3 Previous and Concomitant Medication

Medications taken since birth and concomitant medications will be coded according to the World Health Organization (WHO) drug dictionary, version DDE September 2013 or later. Medications will be summarized using frequency and percentages for each treatment group by drug category and generic name.

3.4 PROTOCOL VIOLATIONS/DEVIATIONS

A protocol violation occurs when the PI fails to adhere to any significant protocol requirement affecting the inclusion, exclusion, subject safety, and primary endpoint criteria. A protocol deviation is any deviation from the protocol that is not a protocol violation. All protocol violations/deviations will be summarized by treatment group and listed by subject.

4 EFFICACY ANALYSIS

The efficacy analysis for this study is for exploratory purposes only. No formal hypothesis testing or statistical modeling will be done.

4.1 EFFICACY POPULATIONS

The ITT population is the efficacy analysis population and is defined as all subjects who were randomized in the study.

4.2 EFFICACY ENDPOINTS

Exploratory efficacy endpoints will be evaluated from the time of lucinactant for inhalation initiation until study completion (non-hypothesis testing) and will include the following:

- Intubation and surfactant administration
- Onset/incidence of bronchopulmonary dysplasia (BPD)
- Survival without BPD at 36 weeks PMA
- Worsening of respiratory status
- Technical performance of the ADS

4.3 STATISTICAL ANALYSIS

All statistical analyses will use summary statistics to describe all endpoints; no statistical testing will be done. All time points will be measured from time of randomization unless otherwise specified.

Categorical variables will be summarized using frequency and percent. Continuous variables will be summarized using n, mean, SE, SD, median, minimum, and maximum. Summary statistics will be presented by treatment group.

4.3.1 Onset of BPD and Survival without BPD

The number and percent of subjects who develop BPD by 36 weeks PCA and the number and percent of subjects who are alive and are without BPD at 36 weeks PCA will be summarized.

4.3.2 Worsening of Respiratory Status

The number of subjects with worsening respiratory status will be summarized. A subject is considered to have worsening respiratory status if they meet at least one of: the need for additional surfactant therapy following exposure to lucinactant for inhalation; a sustained

fraction of inspired oxygen (FiO_2) > 0.50 for > 30 minutes to maintain an oxygen saturation (SpO_2) > 90%; arterial CO_2 (PCO_2) > 65 mmHg on ≥ 2 consecutive occasions; persistent, arterial pH < 7.20; any sustained apneic event; intubation for any reason (except for elective surgical procedures); nCPAP > 7 cmH₂O; initiation of intermittent positive pressure breaths using inflating pressures above the set CPAP pressure administered manually or mechanically through any patient interface; death while on study; or the study PI determines that the subject has worsening respiratory status based on their best clinical judgment.

Worsening respiratory status will be categorized as early (within 72 hours after birth) or late (more than 72 hours but within 7 days after birth) worsening.

4.3.3 Intubation and Surfactant Administration

The number of subjects intubated for mechanical ventilation and for all reasons (eg, surfactant administration) will be summarized. In addition, the time to intubation for mechanical ventilation and the time to any intubation will be summarized using n, mean, SE, SD, median, minimum, and maximum.

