3.3 Safety Evaluations

The following measures are to be documented in the electronic case report form (eCRF) in accordance with timings outlined in Appendix 2 and Section 7:

1. Survival (date and time of death if applicable)

2. AEs, including ADEs
 - To include: nasal excoriations by examination (≥ 24 hours to ≤ 7 days following aerosol exposure) and evidence of lung air leak (especially pneumothorax) (Section 7.1.8)
 - To be categorized as a peri-dosing events if onset of event is ≤ 2 hours from the time of initiating administration of lucinactant for inhalation [Section 9])
3. Signs consistent with worsening respiratory status (Section 7.5)
4. Concomitant medications (Section 7.3)
5. Use of respiratory support and supplemental oxygen (Section 7.6), to include:
 - Need for endotracheal intubation and mechanical ventilation
 - Need for intermittent positive pressure breaths using inflating pressures above the set CPAP pressure administered manually or mechanically through any patient interface
 - nCPAP and fraction of inspired oxygen (FiO₂) requirements (Section 5.4.1), (Section 7.6.2)
6. Complications of prematurity (ie, IVH, periventricular leukomalacia [PVL], pulmonary hemorrhage, NEC, patent ductus arteriosus [PDA], sepsis, ROP, BPD)
7. Physical examinations (Section 7.1.6)
8. Tolerability of lucinactant for inhalation
9. Incidence leading to withdrawal from study
10. Incidence of air leak
11. Assessments of the following:
 - a) PCO₂ (Section 7.1.5)
 - b) Serum electrolyte measurements (Section 7.1.7)
 - c) Body weight (Section 7.1.2)
 - d) Vital signs (Section 7.1.1)
 - e) Gastric liquid volume (Section 7.1.9)
 - f) Defecation (Section 7.1.10)
 - g) Oxygen (O₂) saturation, as determined by pulse oximetry (SpO₂) (Section 7.1.3)
 - h) Chest radiography, as applicable (Section 7.1.8)

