7.6.2 Documentation During Primary and Extended Observation Period

From the time of randomization until completion of Study Day 7 the following must be evaluated and documented in the study eCRF:

1. Mechanical ventilation: date and time of initiation and discontinuation, the mode, mean airway pressure, respiratory rate, set tidal volume (if appropriate), and FiO₂
 - To be documented every 12 hours (\pm 1 hour) until mechanical ventilation has been discontinued for > 24 hours
2. Pressure support (to include nCPAP): date and time of initiation and discontinuation, PIP, respiratory rate, CPAP, flow rate, and FiO₂, as appropriate.
 - Primary Observation Period: document at 1, 3 (\pm 15 minutes), 6, 12 (\pm 1 hour), 18, 24, 36, and 48 hours (\pm 2 hours) post-randomization
 - Extended Observation Period: document every 12 hours (\pm 1 hour) until nCPAP has been discontinued for > 24 hours
3. Supplemental oxygen (FiO₂ > 21%): date and time of initiation and discontinuation, mode of delivery (eg, nasal cannula, oxygen hood), and FiO₂, as appropriate.

- After the administration of lucinactant for inhalation, FiO_2 must be documented every 12 hours (± 1 hour) until supplemental oxygen has been discontinued for > 24 hours

4. Intubation: the date and time of intubation for any reason must be documented.

If respiratory support or oxygen delivery is reinitiated following discontinuation, then parameters must again be captured every 12 hours until discontinuation.

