13.1 Statistical and Analytical Plans

The statistical analysis will be based on all randomized subjects in the study, ie, the Intent-to-Treat (ITT) population. In addition, all evaluable subjects will be analyzed for efficacy signals. Evaluable subjects are those in whom complications of prematurity (eg, PDA, IVH, sepsis,) do not preclude assessment of efficacy signals (eg, improvement in oxygenation, need for intubation and IMV). For all variables, summary statistics will be provided by dosing group, including frequency count and percentage for discrete or categorical variables, and mean, standard deviation, median, minimum, and maximum for continuous variables. In addition, time-to-event variables will be summarized using Kaplan-Meier methodology. Incidence and rates of death, BPD, survival without BPD, and worst-stage ROP at 36 weeks PMA will be summarized.

If no values are recorded in a given eCRF data field, they will be treated as missing and will not be imputed.

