8.3 DETAILS ON STATISTICAL METHODS

Not applicable for this study.

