11 LIST OF TABLES

Table	Title
1.1	Subject Disposition – Study Populations – All Subjects
1.2	Subject Disposition – Study Completion/Termination Status – All Subjects
1.3	Subject Disposition – Protocol Deviations/Violations – All Subjects
2.1	Subject Demographics – Intent-to-Treat Population
2.2	Medical Information – Maternal History – Intent-to-Treat Population
2.3	Medical Information – Birth History – Intent-to-Treat Population
3.1	Concomitant Medications – Safety Population
3.2	Number of Treatments Received – Safety Population
4.1.1	Exploratory Efficacy Analysis – Early Worsening of Respiratory Status Criteria – Intent-to-Treat Population
4.1.2	Exploratory Efficacy Analysis – Late Worsening of Respiratory Status Criteria – Intent-to-Treat Population
4.2	Exploratory Efficacy Analysis – BPD and Survival Without BPD at 36 Weeks PMA – Intent-to-Treat Population
4.3	Exploratory Efficacy Analysis – Time until Intubation for Mechanical Ventilation – Intent-to-Treat Population
4.4	Exploratory Efficacy Analysis – Time until Any Intubation – Intent-to-Treat Population
5.1	Investigational Device – Technical Performance – Safety Population
5.2	Investigational Device – Early Termination of Treatment – Safety Population
6.1	Peri-Dosing Adverse Events – Safety Population
6.2	Air Leak – Safety Population
6.3.1	Treatment-Emergent Adverse Events by System Organ Class and Preferred Term – Safety Population
6.3.2	Treatment-Emergent Adverse Events by System Organ Class, Preferred Term, and Severity – Safety Population
6.3.3	Treatment-Emergent Adverse Events by System Organ Class, Preferred Term, and Relationship – Safety Population
6.3.4	Treatment-Emergent Adverse Events by Severity and Relationship to Study Drug – Safety Population
6.3.5	Treatment-Emergent Adverse Events in Descending Order by Total Active Group – Safety Population
6.4.1	Serious Adverse Events by Preferred Term Displayed in Descending Order by Total Active Group – Safety Population
6.5.1	Adverse Device Effects by Treatment Group – Safety Population
6.6	All-Cause Mortality – Safety Population

- 7.1.1 Clinical Assessments – Vital Signs – Body Temperature – Observed Values and Change from Baseline – Safety Population
- 7.1.2 Clinical Assessments – Vital Signs – Respiration Rate – Observed Values and Change from Baseline – Safety Population
- 7.1.3 Clinical Assessments – Vital Signs – Heart Rate – Observed Values and Change from Baseline – Safety Population

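### SAP 4.3.3 drops the Kaplan-Meier summary that Protocol 13.1 calls for and has no censoring rule, so time to intubation describes only intubated infants in tables labelled Intent-to-Treat

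*SAP*

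**What the plan says.** Protocol 13.1 lists counts, percentages, means, SDs, medians and ranges for all variables and then adds: "In addition, time-to-event variables will be summarized using Kaplan-Meier methodology". The sentence is general and names no variable.

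SAP 4.3.3 covers intubation in two steps. It first gives the count: "The number of subjects intubated for mechanical ventilation and for all reasons (eg, surfactant administration) will be summarized". It then says that "the time to intubation for mechanical ventilation and the time to any intubation will be summarized using n, mean, SE, SD, median", minimum and maximum.

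No other part of the SAP supplies the missing method:

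- SAP 4.3 fixes the time origin ("All time points will be measured from time of randomization unless otherwise specified") and repeats the same descriptive statistics.
- SAP 8.3, the place for method details, reads "Not applicable for this study".
- SAP 4.4 rules out imputation or adjustment for missing data, and Protocol 13.1 also leaves blank fields unimputed.
- The SAP list of tables and figures contains no Kaplan-Meier output. Table 4.3 (intubation for mechanical ventilation) and Table 4.4 ("Time until Any Intubation") are both labelled Intent-to-Treat, which SAP 4.1 defines as all randomised subjects.

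**The concern.** Time to intubation is a time-to-event variable, and Tables 4.3 and 4.4 are the only time-to-event tables the SAP lists. If the protocol's Kaplan-Meier sentence does not apply to them, it has no listed output at all.

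The omission changes what the tables describe. A mean or SD needs a number for every infant counted, and an infant who is never intubated has none. Without censoring or imputation, the summary shrinks to the infants who had the event. A treatment that prevents intubations changes who is in that subgroup, so its mean time has no fixed relation to benefit. Nor do the documents say how to treat infants who die, are transferred or are discharged before any intubation, although each of these ends follow-up under the protocol's study design.

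Avoiding intubation is the product's stated rationale, so readers will look at these tables even though they are exploratory.

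**Working it through.** **Figure to reproduce.** There is none. The study has no hypothesis tests (SAP 1.3) and no sample size calculation (SAP 2.2.3).

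**Textual check.**

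| Item | Protocol | SAP |
|---|---|---|
| Method for time-to-event variables | Descriptive statistics plus Kaplan-Meier (13.1) | Descriptive statistics only (4.3, 4.3.3) |
| Censoring or competing-event rule | None | None (8.3 gives no methods) |
| Infants without a value | Missing, not imputed (13.1) | No imputation or adjustment (4.4) |
| Population in Tables 4.3 and 4.4 | – | All randomised (4.1, list of tables) |

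The SAP never says that the summary covers intubated infants only. That is an inference, but no other reading of the last three rows can be programmed.

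**Inputs for the illustration.** Group sizes are 8 per active dose and 32 pooled controls (SAP Executive Summary). The Protocol Summary (Rationale) says that a third to a half of infants on nCPAP deteriorate and go on to need intubation. The 7-day window (T = 168 h), the constant hazard and the halving of the hazard are assumptions. Death, transfer and discharge are left out.

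**1. Mean among the intubated, constant hazard.** Hazard λ = −ln(1−p)/T. Mean time given intubation by T = 1/λ − T(1−p)/p. Restricted mean over all infants = p/λ.

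| Case | p | 1/λ (h) | T(1−p)/p (h) | Mean, intubated only (h) | Restricted mean, all infants (h) |
|---|---|---|---|---|---|
| Lower rate, no effect | 0.333 | 414.3 | 336.0 | 78.3 | 138.1 |
| Lower rate, hazard halved | 0.184 | 828.7 | 747.5 | 81.2 | 152.1 |
| Higher rate, no effect | 0.500 | 242.4 | 168.0 | 74.4 | 121.2 |
| Higher rate, hazard halved | 0.293 | 484.7 | 405.6 | 79.2 | 142.0 |

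The incidence falls by 15 or 21 percentage points. The mean among the intubated moves by only 3 to 5 h, while the restricted mean over all infants moves by 14 to 21 h.

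**2. How many of 8 infants have a time.** Binomial with n = 8: P(X ≤ 1) = (1−p)^8 + 8p(1−p)^7.

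| p | Expected intubated (8p) | P(0 or 1 intubated) |
|---|---|---|
| 0.333 | 2.7 | 0.195 |
| 0.500 | 4.0 | 0.035 |
| 0.184 | 1.5 | 0.553 |
| 0.293 | 2.3 | 0.270 |

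With 0 or 1 intubated infants, no SD or SE can be computed.

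**3. Direction of the mean.** Suppose 50% of controls are intubated, half of them early and half late, and the drug brings this to 37.5%. With assumed times of 12 h and 72 h:

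- Control: (25×12 + 25×72)/50 = 42 h.
- Half of the late intubations prevented: (25×12 + 12.5×72)/37.5 = 32 h.
- Half of the early intubations prevented: (12.5×12 + 25×72)/37.5 = 52 h.

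Other assumed times behave the same way: 6/48 h gives 27 h, then 20 or 34 h; 24/96 h gives 60 h, then 48 or 72 h. The same benefit can look like faster or slower failure. A control rate of 33% falling to 25% gives the same means, because the early/late split is unchanged.

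**The case against.** The omission itself is not in dispute. The case for giving it little weight runs as follows.

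- **Exploratory status.** No test, safety review or enrolment hold uses time to intubation, and it is not among the efficacy endpoints in Protocol 3.4.1. This stands, and it limits the consequence to interpretation. Kaplan-Meier is itself a descriptive summary, though, so a plan without testing is no reason to leave it out.
- **The information is largely there.** The number intubated is reported, the n in the time summary would show the reduced denominator, and mechanical ventilation data are listed by subject. Tables 4.1.1 and 4.1.2 cover worsening criteria, including intubation and death, within 72 h and from 72 h to 7 days after birth. This partly offsets the loss. It does not tie timing to the infants still at risk, and it does not settle how death or transfer enters.
- **The figures rest on assumptions.** This is correct. The halved hazard and the two-point event times are invented, and the protocol attaches no 7-day window to its third-to-half figure. The calculation also includes no censoring, and without censoring the Kaplan-Meier estimate at 168 h equals the crude proportion. So the figures illustrate selection on the outcome, not the size of harm from the missing censoring rule.
- **Kaplan-Meier does not cure small numbers.** Also correct. With 8 infants and no censoring, the median is not reached if fewer than 4 are intubated. That chance is 74% at the 33% rate and 36% at the 50% rate with no drug effect, and about 96% and 82% with the hazard halved. What Kaplan-Meier adds is that all 8 infants stay in the denominator.

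**Conclusion.** The concern holds. SAP 4.3.3 departs from Protocol 13.1, and neither document has a rule for infants who leave follow-up without intubation. Followed literally, the SAP puts an outcome-selected summary into tables labelled as covering all randomised infants. These textual points are firm.

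The size is illustrative. Under the constant-hazard assumptions, the summary barely registers a halving of risk. In a dose group of 8, the chance that no SD exists is 4% to 20% without a drug effect and 27% to 55% with the hazard halved. A mean that moves against the benefit is possible, but only under particular assumed timings.

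Because the endpoint is exploratory and the count is reported alongside, this should be corrected before database lock. It does not threaten the safety conclusions.

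**What to change.** In SAP 4.3.3 and Tables 4.3 and 4.4:

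1. Add Kaplan-Meier estimates by treatment group, on all randomised infants and from randomisation, for time to intubation for mechanical ventilation and time to any intubation.
2. Define censoring at discharge, transfer, withdrawal or 36 weeks PMA. State the end of the window as well: SAP 1.2.4.1 stops efficacy evaluation at Study Day 7, whereas SAP 4.2 runs to study completion.
3. State how death before intubation is handled, either as a composite with intubation or as a competing event with cumulative incidence. This goes beyond the protocol sentence, but the estimate is undefined without it.
4. Report estimated proportions at 72 h and 7 days, with the number at risk. Medians will often not be reached.
5. Label any retained mean, SE or SD as referring to intubated infants only.

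If the sponsor prefers to keep only the event-based statistics, the SAP should label them that way and explain the departure from Protocol 13.1.

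The cost is SAP wording and routine programming. Under Protocol 7.6.2, "the date and time of intubation for any reason must be documented", and 7.6.3 continues this from Study Day 8. Date and time of death (3.3) and of transfer or discharge (8.4) are also recorded, so the eCRF does not change.
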